The analysis of the combined imputations for FASB (EF \geq 25 and NYHA=3) resulted in a z=-2.1549 with corresponding P=0.0156.

These imputation analyses by ITT, FASA, or FASB all resulted in similar outcomes. The whole population does not demonstrate statistical significance at a 0.025. The sub group of patients with baseline EF \geq 25 results in a P-value less than 0.05, but slightly above the 0.025 value and the sub-group with EF \geq 25 and NYHA=3 achieves statistical significance with P<0.025.

XIII. Secondary Effectiveness Analyses

The mean AT and PVO2 at Baseline, 24 weeks and 50 weeks for the CC population are given in the table below.

Table XIII.1a Mean AT and PVO2 at Study Time Points

Variable	Time	Control Mean (SD) N Med (Min, Max)	Optimizer Mean (SD) N Med (Min, Max)	P-value
AT	Baseline	10.97 (2.18) 207 10.73 (5.40, 17.05)	10.95 (2.24) 201 10.60 (5.29, 16.92)	0.9528 ¹
	24 Week	10.96 (2.20) 158 10.83 (6.24, 19.61)	10.87 (2.45) 169 10.49 (5.01, 19.82)	0.7346 ¹
	24 Week Difference From Baseline	-0.14 (2.14) 154 -0.23 (-4.99, 9.34)	-0.14 (2.23) 159 -0.25 (-6.47, 8.94)	0.5040 ³
	50 Week	10.92 (2.49) 148 10.78 (4.10, 20.93)	11.10 (2.56) 163 10.92 (5.40, 21.83)	0.5471 ¹
	50 Week Difference From Baseline	-0.14 (2.64) 146 -0.35 (-6.45, 10.66)	0.01 (2.59) 156 -0.30 (-5.43, 12.25)	0.3158 ³
PVO2	Baseline	14.71 (2.92) 211 15.02 (8.54, 22.61)	14.73 (3.06) 214 14.48 (8.43, 23.02)	0.9245 ¹
	24 Week	14.54 (3.56) 169 14.47 (6.30, 27.95)	14.94 (3.62) 179 14.47 (7.63, 27.49)	0.3008 ¹
	24 Week Difference From Baseline	-0.41 (2.90) 168 -0.50 (-7.68, 11.60)	0.24 (3.16) 179 -0.04 (-8.17, 11.69)	0.0242 ³
	50 Week	14.59 (3.87) 159 14.47 (6.88, 29.75)	14.72 (3.51) 172 14.47 (8.12, 30.67)	0.7394 ¹
	50 Week Difference From Baseline	-0.44 (3.01) 152 -0.58 (-7.80, 12.06)	-0.08 (3.47) 164 -0.21 (-6.87, 17.45)	0.2330 ³

¹Two-sided equal variance Student's t-test.

²Two-sided unequal variance Student's t-test

³One-sided equal variance Student's t-test

The responder analyses for the CC population at 24 and 50 weeks are provided in the table below.

Table XIII.1b Responder Analysis (20% or Greater improvement from Baseline) at Study Time Points

Variable	Time	Control n/N (%)	Optimizer n/N (%)	P-value ¹
AT	24 Week	18/154 (11.69)	28/159 (17.61)	0.0932
	50 Week	21/146 (14.38)	37/156 (23.72)	0.0275
PVO2	24 Week	23/168 (13.69)	31/179 (17.32)	0.2169
	50 Week	24/158 (15.19)	31/172 (18.02)	0.2944

¹One-sided Fisher's exact test

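### Table XIII.1a, 50-week peak VO2 change: the printed P-value (0.2330) does not follow from the printed summary statistics (about 0.163), and the Ns (152/164) differ without explanation from Table XIII.1b (158/172)

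*Combined protocol and SAP*

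**What the plan says.** All entries are in section XIII of the statistical report. The quoted cells begin just after any leading minus sign and stop before the closing bracket.

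- Table XIII.1a, PVO2, 50-week change. Control, with a negative mean: "0.44 (3.01) 152 -0.58 (-7.80, 12.06". Optimizer, with a negative mean: "0.08 (3.47) 164 -0.21 (-6.87, 17.45". The printed P is 0.2330 with footnote mark 3, which reads "³One-sided equal variance Student's t-test".
- Table XIII.1a, PVO2 level at 50 weeks. Control: "14.59 (3.87) 159 14.47 (6.88, 29.75". Optimizer: "14.72 (3.51) 172 14.47 (8.12, 30.67". So 159 and 172 patients have a week-50 value.
- Table XIII.1b, titled "Responder Analysis (20% or Greater improvement from Baseline) at Study Time Points", gives 50-week PVO2 responders as 24/158 and 31/172, P = 0.2944. It is introduced by "The responder analyses for the CC population at 24 and 50 weeks are provided in the table below".
- Table XIII.1a is also introduced as the CC population. Section VII defines CC by having a 24-week endpoint.
- Table VI.4, footnote 6: two Control patients and one Optimizer patient lack a core-laboratory baseline PVO2.

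No footnote explains why the change row has fewer patients than the responder row.

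**The concern.** The mean change and the 20% response at week 50 need the same two measurements, baseline and week-50 PVO2. Within one population they should rest on the same patients, but here they differ by 6 Control and 8 Optimizer patients. Separately, the P-value cannot be obtained from the statistics printed beside it. A reader therefore cannot tell which patients the estimate describes, or whether the estimate and the test belong together.

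Peak VO2 change is among the protocol's secondary efficacy analyses (sections IV.A and IX.A.4), although no time point is named for it there. This row is the only whole-population mean change in PVO2 reported at 50 weeks, so it should be reproducible from its own entries.

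**Working it through.** **Step 1. The P-value from its own row.** Inputs from Table XIII.1a: Control -0.44 (3.01), n = 152; Optimizer -0.08 (3.47), n = 164.

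- Pooled variance = (151 × 3.01² + 163 × 3.47²) / 314 = (1368.08 + 1962.67) / 314 = 10.61, so the pooled SD is 3.257.
- Standard error = 3.257 × √(1/152 + 1/164) = 0.3667.
- t = (-0.08 + 0.44) / 0.3667 = 0.982 on 314 degrees of freedom.
- One-sided P = 0.1635. The printed figure is 0.2330.

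**Step 2. Can another choice explain 0.2330?**

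| Variant | P |
|---|---|
| One-sided, equal variance, every mean and SD moved by ±0.005 | 0.157 to 0.171 |
| One-sided, Welch | 0.1622 |
| Two-sided, equal variance | 0.3270 |
| Two-sided, Welch | 0.3244 |
| One-sided, equal variance, same means and SDs, N = 158/172 | 0.158 (0.151 to 0.166 with rounding) |

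None of these gives 0.2330.

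**Step 3. Is the method right?** The same one-sided equal-variance formula reproduces the other change rows within rounding.

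| Row | Recomputed | Printed |
|---|---|---|
| AT, 24-week change | 0.500 | 0.5040 |
| AT, 50-week change | 0.309 | 0.3158 |
| PVO2, 24-week change | 0.0236 | 0.0242 |
| PVO2, 50-week change, EF ≥ 25 (Table XIV.2a) | 0.0443 | 0.0436 |
| PVO2, 50-week change, EF ≥ 25 and NYHA III (Table XIV.4a) | 0.0177 | 0.0174 |

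**Step 4. The Ns (Control/Optimizer).**

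| Row | N, mean change | N, responders |
|---|---|---|
| AT, 24 weeks | 154/159 | 154/159 |
| AT, 50 weeks | 146/156 | 146/156 |
| PVO2, 24 weeks | 168/179 | 168/179 |
| PVO2, 50 weeks | 152/164 | 158/172 |
| PVO2, 50 weeks, EF ≥ 25 | 81/100 | 81/100 |

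Only the 50-week whole-population PVO2 row disagrees. The 24-week Control cell, with a negative mean, reads "0.41 (2.90) 168 -0.50 (-7.68, 11.60", and its N equals the denominator of 23/168 in Table XIII.1b.

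The 158/172 denominators were really used for the responder test: one-sided Fisher on 24/158 against 31/172 gives 0.2944, as printed, whereas 152/164 would give 0.281.

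They also agree with the data available. With 159 and 172 week-50 values, and at most 2 and 1 baseline values missing, at least 159 − 2 = 157 and 172 − 1 = 171 changes can be derived. The change row is short of the responder row by 158 − 152 = 6 and 172 − 164 = 8, together 14 of 330 (4.2%).

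**The case against.** The strongest defence is the definition of CC. A patient with baseline and week-50 values but no 24-week endpoint is outside that population, so a strict CC analysis at week 50 could properly have fewer than 158/172 patients. This stands to the extent that the documents do not prove 158/172 to be the required set.

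It does not rescue the row:

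- Table XIII.1b carries the same CC label and uses 158/172.
- The baseline PVO2 row of Table XIII.1a has 211/214 patients, so the table is not strictly limited to CC.
- If the 24-week endpoint means the AT change, only 159 Optimizer patients have one, fewer than the 164 in this row.
- In Table XIV.2a, 100 Optimizer patients have a 50-week PVO2 change but only 99 have a 24-week PVO2, so that CC table is not restricted by 24-week PVO2 either.
- No choice of N among those tested brings the printed means and SDs to P = 0.2330.

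A reader might also infer that the printed effect is inflated. With the printed SDs, P = 0.2330 corresponds to a difference of 0.26 (N = 158/172) to 0.27 (N = 152/164), against the printed 0.36. That inference needs the P-value to be the reliable entry and these SDs to belong to the patients behind it. The documents support neither assumption. If the P-value is a slip, 0.36 is not inflated. If it came from another patient set, these SDs do not apply.

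Nor is this the only whole-population PVO2 result at 12 months: the row above it gives the week-50 level means, 14.59 and 14.72, P = 0.7394.

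**Conclusion.** The row is internally inconsistent in two respects. The printed P of 0.2330 should be about 0.163 (0.157 to 0.171) if the printed means, SDs and Ns are right. The Ns differ from the responder table by 6 Control and 8 Optimizer patients without a stated reason. The first result rests only on the footnoted test and the printed figures; the second rests on both tables describing the same population, as their introductions say.

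The documents do not show which entry is wrong. A P-value run on one patient set beside means from another is possible, and so is a transcription error in any cell. It would go too far to say that 14 patients were wrongly dropped, or that the corrected difference will be smaller: the means and SDs on 158/172 are not reported, so the result for that set cannot be computed.

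The point is minor. Both P-values are well above 0.025, and neither the text of section XIII nor the closing summary of section XIV relies on this row.

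**What to change.** State which analysis set applies at week 50: CC as defined in section VII, or all patients with baseline and week-50 values (apparently 158 Control and 172 Optimizer). Re-derive the mean, SD, N and P of the 50-week PVO2 change row from that single set. Use the same set for the 50-week PVO2 responders in Table XIII.1b, and footnote any patients with both values who are left out, with the reason. If strict CC is chosen, say which 24-week endpoint defines it and apply the rule to the other week-50 rows as well.

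The cost is a re-run of one table row from existing data, plus the matching responder row, and any other week-50 row affected, if strict CC is adopted. No new data are needed.

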Pacemaker implantation has been well characterized and is the standard of care for treatment of certain types of cardiac rhythm disorders. The literature related to this therapy is voluminous and readily available. References specific to CCM signal application are listed in **Appendix A**. Cardiac resynchronization therapy (CRT) is applicable to heart failure patients with conduction abnormalities manifested as an increased QRS duration on the body surface electrocardiogram. The clinical studies in which CRT has been evaluated have provided important information for how to conduct studies of CCM signal application and are therefore relevant to the present investigation.

III. Trial Objectives and Purpose

The objective of this investigation is to evaluate the safety and effectiveness of the OPTIMIZER™ System with active fixation leads in subjects with moderate to severe heart failure. Safety and effectiveness endpoints are provided in Section IV below.

IV. Trial Design

A. Primary and secondary endpoints to be measured during the trial

1. The primary effectiveness endpoint of this study, which will be evaluated at the end of six months following the date of scheduled implantation, shall consist of the following parameter:

Improvement in exercise tolerance, as quantified by ventilatory threshold (VT) measured on cardiopulmonary exercise stress testing (CPX), and evaluated by a blinded core lab. Individual patient response will be based on a ≥ 1 mlO₂/min/kg improvement in VT at 6-months compared to baseline.

2. The secondary efficacy endpoints shall be:
 - a. Improvement in heart failure class, as assessed by the New York Heart Association (NYHA) classification. NYHA classification shall be assigned by:
 - i. blinded on site clinicians according to their standard clinical practice
 - ii. by a blinded core lab that evaluates patient responses to a standardized questionnaire.¹
 - b. Improvement in quality of life, as assessed by the Minnesota Living with Heart Failure (MLWHF) Questionnaire.
 - c. Improvement in exercise tolerance, as quantified by the six minute hall walk test (6MW).
 - d. Improvement in left ventricular ejection fraction as assessed by echocardiography in a blinded core lab.
 - e. Changes in left ventricular size as indexed by echocardiographically determined end-diastolic dimension determined by a blinded core lab.

- f. Improvements in peak VO₂ consumption and ventilatory efficiency determined on CPX testing.

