This is a multicenter, prospective, randomized, study in 418 subjects with moderate to severe heart failure despite optimal medical therapy. The study will include a baseline eligibility evaluation followed by randomization to either receive or not receive an OPTIMIZER™ device implant. All patients will be followed for twelve-months (**Figure 1**). Evaluation of subjects will be documented on electronic case report forms and will include the tests and procedures listed in **Table 1**.

FIGURE 1. Study Overview

[figure not shown]

TABLE 1. Schedule of Events

Test	Screening	Baseline	Implant*	Follow-Up Schedule (relative to Study Start Date [§])						
				Week 2 ±2 days [§]	+4±1 Week	+12±2 Weeks	+24±2 Weeks	36±2 Weeks	50±2 Weeks	Every 6 Months*
Informed Consent	X									
History	X			X	X	X	X	X	X	X
NYHA Class (Blinded site clinician assessment)	X					X	X		X	
NYHA Class (Blinded Core Lab Questionnaire)	X					X	X		X	
Medications	X			X	X	X	X	X	X	
Physical Examination	X			X	X	X	X	X	X	
12-Lead EKG		X								
Echocardiogram		X				X	X		X	
MLWHFQ		X				X	X		X	
6-minute walk		X				X	X		X	
Cardiopulmonary Stress Test		X				X	X		X	
24 hour Holter Monitor		X				X	X			
Urine pregnancy test		X					X		X	
Eligibility determination		X								
Randomization		X								
OPTIMIZER™ System Implant*			X							
Chest X-ray*			X							
Optimizer Device Interrogation / Programming*			X	X	X	X	X	X	X	X
ICD Device Interrogation (episodes of VT/VF)				X		X	X	X	X	
Adverse Events, Hospitalizations, and Procedures (as needed) /OPTIMIZER device-related SAEs after 50-wks		X	X	X	X	X	X	X	X	X

[§] Study Start Date: After completion and satisfying all entry criteria, a date shall be scheduled for OPTIMIZER System implant. This date shall serve as the start date for all subjects. For subjects randomized to CCM Treatment, the OPTIMIZER system shall be implanted on this date. For subjects randomized to the Control group in whom an ICD implant is planned, the Study Start Date shall be the day of the ICD implant. For subjects randomized to the Control group who do not undergo an ICD implant, the scheduled implant shall be cancelled and this date shall serve as the Study Start Date from which all future follow-up visits are scheduled.

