⁴ A difference in VT of 1 ml O₂/kg/min is justified as being clinically significant based on prior studies of cardiac resynchronization therapy showing that there is an approximately 1 ml O₂/kg/min change in response to that approved therapy (Auricchio et al. J Am Coll Cardiol 2003;42:2109-16)

The secondary analyses will include:

- a. Comparison between groups of the change from baseline in New York Heart Association (NYHA) classification. NYHA classification shall be assigned by:
 - i. blinded on site clinicians according to their standard clinical practice
 - ii. by a blinded core lab that evaluates patient responses to a standardized questionnaire.⁵
- b. Comparison between groups of the changes from baseline in quality of life, as assessed by the Minnesota Living with Heart Failure (MLWHF) Questionnaire.
- c. Comparison between groups of the change from baseline in exercise tolerance, as quantified by the six minute hall walk test (6MW).
- d. Comparison between groups of the change from baseline in left ventricular ejection fraction as assessed by echocardiography in a blinded core lab.
- e. Comparison between groups of the change from baseline in left ventricular size as indexed by echocardiographically determined end-diastolic dimension determined by a blinded core lab.
- f. Comparison between groups of the change from baseline in peak VO₂ and ventilatory efficiency determined on CPX testing.
- g. Comparisons of treatment effects separately in subjects whose CHF etiology is ischemic or non-ischemic
- h. Comparison between groups of the change from baseline in medical treatment for heart failure (either up or down titration of doses or changes in the types of medications prescribed).

⁵ **Kubo SH, Schulman S, Starling RC, Jessup M, Wentworth D and Burkhoff D.** Development and validation of a patient questionnaire to determine New York Heart Association classification. *J Card Fail* 10: 228-235, 2004.

- i. Comparison within the treatment group of the primary and secondary safety and efficacy outcome measures in subjects with and without a pacemaker or ICD.
 - j. Evaluation of the impact of CCM voltage on primary and secondary efficacy and safety outcome measures.
5. Other Analyses

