Any FIX-HF-5 Study Investigator not participating in the FIX-HF-5C Study that wishes to use an OPTIMIZER IVs IPG for a revision/replacement procedure must request an “Approved Deviation From Protocol” from their IRB, the Sponsor and the FDA.

Consent Materials

A template informed consent addendum is attached for all subjects currently active in the FIX-HF-5 protocol.

The Statistical Analysis Report for the FIX-HF-5 Clinical Study of the OPTIMIZER System in Patients with Medically Refractory Heart Failure

By

[name].

I. Introduction

Moderate to severe heart failure is associated with disability that significantly limits exercise tolerance and is associated with poor quality of life. The OPTIMIZER System delivers cardiac contractility modulation, non-excitatory signals during the myocardial absolute refractory period synchronized with locally sensed electrical activity, intended to improve symptoms in treated subjects.

The statistical analysis below provides a detailed description of the analyses conducted, hypotheses tested, the precise statistical methods used and the populations analyzed. The analysis methods provide a thorough evaluation of the OPTIMIZER System in the population of moderate to severe heart failure subjects.

II. Study Design

This is a multicenter, randomized, prospective, parallel group clinical trial to evaluate the safety and efficacy of the OPTIMIZER™ System with active fixation leads in subjects with moderate to severe heart failure. Four hundred and twenty eight (428) subjects from 50 centers in the US were randomized with equal probability to implantation of the OPTIMIZER™ System in combination with optimal medical treatment (OMT) for heart failure or to OMT alone. Randomization used permuted blocks of four and was stratified by center and etiology of heart failure (ischemic versus non-ischemic cardiomyopathy). The nature of the treatment and requirement for one-year follow up precluded blinding of subjects and their treating clinicians, however, safety data were adjudicated by an independent committee of physician experts according to pre-specified criteria.

III. Objective

The objective of this investigation was to evaluate the safety and effectiveness of the OPTIMIZER™ System with active fixation leads in subjects with moderate to severe heart failure.

IV. Study Sites and Patient Distribution

The distribution of patients by study site and treatment group is given in the table below.

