Note that the responder analysis for 24 weeks has a P-value of less than 0.1 and for 50 weeks has a P-value that is near 0.025.

XIV. Additional Analyses

Analyses of additional endpoints are presented below. The means for the quality of life instrument, the MLWHFQ, the NYHA, and the 6 minute walk test (MWT) are provided at 24 and 50 weeks below.

Table XIV.1a Mean AT and PVO2 at Study Time Points

Variable	Time	Control Mean (SD) N Med (Min, Max)	Optimizer Mean (SD) N Med (Min, Max)	P-value
MLWHFQ	Baseline	57.38 (22.62) 213 59.0 (1.0, 102.0)	60.49 (23.00) 215 64.0 (0.0, 100.0)	0.1595 ¹
	24 Week	52.08 (23.84) 184 53.5 (0.0, 105.0)	45.33 (24.43) 196 46.0 (0.0, 97.0)	0.0068 ¹
	24 Week Difference From Baseline	-5.72 (21.03) 184 -6.0 (-74.0, 68.0)	-15.38 (19.55) 196 -12.5 (-81.0, 25.0)	<0.0001 ³
	50 Week	51.10 (23.57) 173 53.0 (1.0, 101.0)	42.75 (25.66) 183 42.0 (0.0, 101.0)	0.0015 ¹
	50 Week Difference From Baseline	-7.32 (20.66) 173 -6.0 (-81.0, 87.0)	-17.60 (22.68) 183 -15.0 (-81.0, 43.0)	<0.0001 ³
NYHA	Baseline	3.13 (0.35) 213 3.0 (2.0, 4.0)	3.09 (0.28) 215 3.0 (3.0, 4.0)	0.1650 ²
	24 Week	2.81 (0.71) 183 3.0 (1.0, 4.0)	2.53 (0.73) 191 3.0 (1.0, 4.0)	0.0002 ²
	24 Week Difference From Baseline	-0.32 (0.73) 183 0.0 (-2.0, 1.0)	-0.54 (0.72) 191 0.0 (-3.0, 1.0)	0.0015 ³
	50 Week	2.67 (0.78) 174 3.0 (1.0, 4.0)	2.48 (0.85) 185 3.0 (1.0, 4.0)	0.0232 ²
	50 Week Difference From Baseline	-0.47 (0.83) 173 0.0 (-3.0, 1.0)	-0.61 (0.86) 185 -1.0 (-3.0, 1.0)	0.0598 ³
6 MWT	Baseline	323.99 (92.44) 212 321.0 (80.0, 600.0)	326.38 (82.10) 215 330.0 (95.0, 525.0)	0.7771 ¹
	24 Week	335.13 (106.99) 173 340.0 (75.0, 730.0)	347.68 (95.47) 190 349.0 (90.0, 585.0)	0.2384 ¹
	24 Week Difference From Baseline	8.61 (85.08) 173 7.0 (-375.0, 457.0)	19.41 (80.62) 190 15.0 (-316.0, 301.0)	0.1079 ³
	50 Week	337.31 (109.49) 162 342.0 (80.0, 823.0)	348.97 (98.34) 181 357.0 (55.0, 615.0)	0.2996 ¹
	50 Week Difference From Baseline	10.51 (87.16) 162 14.0 (-375.0, 365.0)	20.22 (83.14) 181 13.0 (-220.0, 285.0)	0.1449 ³

¹Two-sided equal variance Student's t-test.

²Two-sided unequal variance Student's t-test

³One-sided equal variance Student's t-test

A responder analysis with response being defined as -10 or more points for the MLWHFQ, -1 or more classes for the NYHA, and 40 meters or more for the 6 MWT.

Table XIV.1b Responder Analysis at Study Time Points

Variable	Time	Control n/N (%)	Optimizer n/N (%)	P-value ¹
MLWHFQ ²	24 Week	77/184 (41.85)	110/196 (56.12)	0.0037

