	50 Week	73/173 (42.20)	112/183 (61.20)	0.0002
NYHA ³	24 Week	63/183 (34.43)	94/191 (49.21)	0.0026
	50 Week	80/174 (45.98)	97/185 (52.43)	0.1320
6 MWT ⁴	24 Week	51/173 (29.48)	65/190 (34.21)	0.1970
	50 Week	51/162 (31.48)	69/181 (38.12)	0.1201

¹One-sided Fisher's Exact Test

²Responder is a 10 or more point improvement from baseline.

³Responder is a 1 or more point improvement from baseline.

⁴Responder is a 40 or more meters improvement from baseline.

Note that there are higher proportions of responders in the Optimizer group for all of the endpoints and time periods. The P-value for patients experiencing a 10 or more point decline in the MLWHFQ at both 24 and 50 weeks are highly statistically significant and NYHA at 24 weeks.

The means for the 24 and 50 week changes in AT and PVO2 are presented for the sub-group with EF \geq 25 for the CC population in the table below.

Table XIV.2a Mean AT and PVO2 at Study Time Points in Sub-group with Baseline EF \geq 25

Variable	Time	Control Mean (SD) N Med (Min, Max)	Optimizer Mean (SD) N Med (Min, Max)	P-value
AT	Baseline	11.17 (2.30) 112 10.74 (5.40, 17.05)	10.68 (2.12) 110 10.39 (5.29, 16.08)	0.1035 ¹
	24 Week	10.89 (2.11) 80 10.80 (6.24, 15.50)	11.00 (2.45) 94 10.46 (5.01, 19.82)	0.7542 ¹
	24 Week Difference From Baseline	-0.44 (1.93) 79 -0.38 (-3.79, 5.64)	0.04 (2.32) 88 -0.15 (-4.65, 8.94)	0.0745 ²
	50 Week	11.00 (2.31) 77 10.97 (4.10, 17.54)	11.11 (2.36) 95 11.16 (5.40, 20.62)	0.7525 ¹
	50 Week Difference From Baseline	-0.27 (2.38) 77 -0.39 (-5.32, 6.62)	0.23 (2.41) 91 0.09 (-5.05, 8.31)	0.0878 ²
	PVO2	Baseline	14.95 (2.83) 112 15.09 (8.68, 22.61)	14.59 (2.95) 117 14.48 (8.43, 20.96)
24 Week		14.21 (3.02) 89 14.10 (6.30, 20.37)	14.99 (3.48) 99 14.84 (7.63, 27.49)	0.1020 ¹
24 Week Difference From Baseline		-1.00 (2.47) 89 -0.96 (-6.54, 6.01)	0.32 (3.04) 99 -0.03 (-6.58, 11.69)	0.0006³
50 Week		14.63 (3.46) 81 14.43 (6.88, 24.51)	14.73 (3.23) 100 14.75 (8.12, 27.19)	0.8446 ¹
50 Week Difference From Baseline		-0.68 (2.93) 81 -0.55 (-6.40, 7.05)	0.08 (3.00) 100 -0.00 (-6.36, 11.38)	0.0436 ²

¹Two-sided equal variance Student's t-test.

²One-sided equal variance Student's t-test

³One-sided unequal variance Student's t-test

The responder analysis for this sub-group in the CC population is presented in the following table.

Table XIV.2b. Responder Analysis (20% or Greater improvement from Baseline) at Study Time Points in Sub-group with Baseline EF \geq 25

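### The protocol plans NYHA change by two blinded assessments, but the report tests one unlabelled NYHA that matches the site grade at baseline, and its 24-week NYHA claims rest on that version alone

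*Combined protocol and SAP*

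**What the plan says.** Protocol IV.A.2.a and IX.A.4.a name two sources for NYHA class. One is "blinded on site clinicians according to their standard clinical practice". The other is assignment "by a blinded core lab that evaluates patient responses to a standardized questionnaire". VII.A repeats the pair. The planned analysis in IX.A.4.a reads "Comparison between groups of the change from baseline in New York Heart Association (NYHA) classification. NYHA classification shall be assigned by", followed by both sources. No section ranks them or says what is concluded if they disagree.

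The schedule of events (protocol Table 1) gives each source its own row. The second is "NYHA Class (Blinded Core Lab Questionnaire", with the same visits as the site row: screening and weeks 12, 24 and 50. Section IV.F.4 lists NYHA among the core-laboratory readings that are meant to limit bias.

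In the statistical report, Table VI.2 labels baseline NYHA as the site grade. Tables XIV.1a to XIV.5b then carry a single NYHA variable with no source named. The text after Table XIV.1b includes it in the statement on results that "are highly statistically significant and NYHA at 24 weeks". The text after Tables XIV.3b and XIV.5b makes the same 24-week claim for EF≥25 and for EF≥25 with NYHA=3, and the closing paragraph repeats the overall claim.

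**The concern.** Two assessments of NYHA were planned and scheduled. One is shown, without a label, and conclusions are drawn from it. A reader of Section XIV cannot tell which grade improved, or that a second planned comparison exists.

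The two grades are different measurements. One follows each clinician's own practice, and the other applies a common questionnaire scored centrally. A patient can be a responder on one and not on the other. If they agree, the NYHA finding is stronger than the report shows. If they disagree, it should be stated more narrowly. The closing statement that Optimizer patients changed more on every measure also cannot be checked for a planned measure that is not reported.

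**Working it through.** **1. The report's own figure.** Table XIV.1b gives 24-week NYHA responders (improvement of one class or more) as 63/183 Control and 94/191 Optimizer. The one-sided Fisher exact test gives P=0.0026, as printed. The other NYHA responder P-values also reproduce:

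| Group | 24 weeks | 50 weeks |
|---|---|---|
| All | 0.0026 | 0.1320 |
| EF≥25 | 0.0105 | 0.1779 |
| EF≥25 and NYHA=3 | 0.0023 | 0.1229 |

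The arithmetic of the report is not in question.

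**2. Which NYHA is it?** Site counts in Table VI.2 for Classes II/III/IV are 1/183/29 (Control, n=213) and 0/196/19 (Optimizer, n=215).

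- Control mean = (2×1 + 3×183 + 4×29)/213 = 667/213 = 3.1315; SD 0.3523; range 2 to 4.
- Optimizer mean = (3×196 + 4×19)/215 = 664/215 = 3.0884; SD 0.2845; range 3 to 4.
- Welch t = (3.1315 − 3.0884)/√(0.3523²/213 + 0.2845²/215) = 0.0431/0.0310 = 1.39; two-sided P = 0.1650.

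The unlabelled baseline rows of Table XIV.1a read "3.13 (0.35) 213 3.0 (2.0, 4.0" and "3.09 (0.28) 215 3.0 (3.0, 4.0", with P=0.1650. A search over whole-number class counts found two Control distributions (1/184/28 and 1/183/29) and one Optimizer distribution (196/19) that fit the rounded mean, SD and range. The first Control option gives P=0.2120. Only the site counts give 0.1650.

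**3. The NYHA=3 subgroup.** Table X.1 has 87 + 109 = 196 Optimizer patients with NYHA=3, equal to site Class III. Control has 85 + 97 = 182. The one Control patient without a core-lab EF could make this 183. The subgroup is therefore also consistent with the site grade.

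**4. How far could the second grade move the result?** No core-lab NYHA data are available, so this is a sensitivity range. It assumes unchanged denominators and shows several patterns of disagreement.

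| Assumed pattern at 24 weeks | Control | Optimizer | One-sided P |
|---|---|---|---|
| As reported | 63/183 | 94/191 | 0.0026 |
| 8 fewer Optimizer responders only | 63/183 | 86/191 | 0.0233 |
| 9 fewer Optimizer responders only | 63/183 | 85/191 | 0.0295 |
| 8 more Control responders only | 71/183 | 94/191 | 0.0271 |
| About 10% fewer in both arms | 57/183 | 85/191 | 0.0053 |
| About 30% fewer in both arms | 44/183 | 66/191 | 0.017 |
| EF≥25: as reported | 27/94 | 47/103 | 0.0105 |
| EF≥25: 3 fewer Optimizer only | 27/94 | 44/103 | 0.0288 |
| EF≥25: 3 fewer Optimizer, 2 fewer Control | 25/94 | 44/103 | 0.013 |

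One-arm changes of 8 or 9 patients cross 0.025 overall. Proportional losses in both arms, even of about 30%, do not.

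**The case against.** **The site assessor is blinded.** The protocol says so in IV.A.2.a, Table 1, VI.A.3.d, VII.A and IX.A.4.a. The report's remark that the trial "precluded blinding of subjects and their treating clinicians" concerns patients and those treating them, not this assessor. A reader might infer that the claims rest on an unblinded grade; the documents do not support that. This objection stands in full.

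**Nothing shows selection.** A reader might suspect that the more favourable grade was chosen, and could attach an inflated false-positive rate to a free choice between two versions. No such choice is documented. The report labels baseline NYHA as the site grade in several tables. It also shows no follow-up results for ejection fraction, end-diastolic dimension, ventilatory efficiency or medication changes, all of which were planned. The missing core-lab rows fit a limited report at least as well. This stands.

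**Neither grade has to decide.** The protocol can be read as asking for both, and it ranks none of its secondary endpoints. This stands, and it is why the remedy is to report both. It does not excuse reporting one.

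**The evidence on source has limits.** The match is shown at baseline only. Follow-up is inferred, because a change from a site baseline implies a site follow-up grade. There is no core-lab distribution to compare. Part of the report between Section IV and the baseline table was not available, though an outcome comparison is unlikely to sit there. These limits are accepted.

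**Conclusion.** The point holds as one of incomplete reporting that affects a conclusion. A comparison planned by two assessments is reported by one, without a label, and the 24-week NYHA claims (overall, EF≥25, and EF≥25 with NYHA=3) rest on that one. The site source is established at baseline by exact reproduction and inferred at follow-up.

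A stronger reading would be that the NYHA result is fragile or would fail on the core-lab grade. That is not supported. P=0.0026 passes 0.025 only under particular assumed patterns, such as a net loss of 9 Optimizer responders with no change in Control, and it stays at 0.0053 when both arms lose about 10%. The direction and size of any disagreement are unknown.

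NYHA is a secondary endpoint and the results appear under additional analyses. The report's primary conclusions do not turn on it.

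**What to change.** 1. In Tables XIV.1a to XIV.5b, label the NYHA rows as site grades, after confirming the source at weeks 24 and 50. State in the text that the NYHA=3 subgroup uses the site grade, if confirmed.
2. Add the planned core-lab NYHA rows beside them, both change from baseline and responders, at 24 and 50 weeks, overall and in the same subgroups. If these data were not collected or are incomplete, say so and give the numbers.
3. Describe the NYHA finding as site-assessed in the text after Tables XIV.1b, XIV.3b and XIV.5b and in the closing paragraph, unless the core-lab comparison also supports it. Limit the statement about all measures to those shown.
4. Do not now make the core-lab grade the sole endpoint. With results known, that would be a post hoc choice, and the core-lab grade has its own weakness: it is scored from the answers of unblinded patients. State this next to the new rows.

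The cost is a few table rows from data that the protocol already schedules, and some rewording. The downside is that the NYHA statement may become weaker.
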